5.1.1 Hypotheses and Statistical Methods for Primary Objectives

5.1.1.1 Hypotheses

Non-inferiority on Tdap vaccine

The objective is to demonstrate that the humoral immune response to the Tdap booster dose administered concomitantly with the first dose of CYD dengue vaccine is non-inferior to the humoral immune response to the Tdap booster dose administered alone 28 days before the first dose of CYD dengue vaccine.

Individual hypotheses on Tdap response for each antigen:

A non-inferiority testing approach will be used to compare geometric mean concentrations (GMCs) for PT, FHA, PRN, FIM2+3, 28 days after the booster dose of Tdap, for each antigen “i” based on the following individual hypotheses:

$$H_0^i: GMC_{Group1}^i / GMC_{Group2}^i \leq \frac{1}{\delta} \Leftrightarrow \log_{10}(GMC_{Group1}^i) - \log_{10}(GMC_{Group2}^i) \leq -\log_{10}(\delta)$$

$$H_1^i: GMC_{Group1}^i / GMC_{Group2}^i > \frac{1}{\delta} \Leftrightarrow \log_{10}(GMC_{Group1}^i) - \log_{10}(GMC_{Group2}^i) > -\log_{10}(\delta)$$

with:

i, antigen {PT, FHA, PRN, FIM 2+3}.

δ , non-inferiority limit is set at 1.5, i.e., 0.176 ($=\log_{10} [1.5]$), for each antigen “i”.

Non-inferiority for antigen “i” will be demonstrated if the lower bound of the 2-sided 95% confidence interval (CI) is greater than δ ($\alpha=2.5\%$ one-sided). For each of the 4 antigens, the statistical methodology will be based on the use of the age-stratified two-sided 95% CI of the ratio of GMCs between groups. The age-stratified CI will be calculated using an analysis of variance (ANOVA) model (type II analysis) of \log_{10} -transformed titers. The age groups (9 to 11 years, 12 to 17 years, 18 to 45 years and 46 to 60 years) will be used as the stratifying factor in the model.

Additionally, a non-inferiority testing approach will be used to compare seroprotection rates of T and D, 28 days after the booster dose of Tdap vaccine. Seroprotection is defined as anti-D and anti-T Ab concentration superior to 0.1 IU/mL.

The individual tested hypotheses for the antigen “i” will be as follows:

$$H_0^i: P_{Group1}^i - P_{Group2}^i \leq -\delta$$

$$H_1^i: P_{Group1}^i - P_{Group2}^i > -\delta$$

with:

i, antigen {T, D}

δ , non-inferiority limit is set at 10% for both T and D.

Non-inferiority for antigen “i” will be demonstrated if the lower bound of the 2-sided 95% CI is greater than $-\delta$.

Global hypotheses for non-inferiority on Tdap response:

The global hypotheses are:

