H_{0G} : Non inferiority of Tdap booster dose co-administered with the first dose of CYD dengue vaccine versus Tdap booster dose administered alone is not demonstrated for at least one antigen.

H_{1G} : Non-inferiority of Tdap booster dose co-administered with the first dose of CYD dengue vaccine versus Tdap booster dose administered alone is demonstrated for all the antigens.

H_0^G : at least one H_0^i not rejected

H_1^G : all H_0^i are rejected

Non-inferiority on CYD dengue vaccine after 1 dose

The objective is to demonstrate that the humoral immune response to the first dose of CYD dengue vaccine administered concomitantly with Tdap booster dose is non-inferior to the humoral immune response to the first dose of CYD dengue vaccine administered sequentially 28 days after the Tdap booster dose.

Individual hypotheses on CYD response after one dose for each serotype:

A non-inferiority testing approach will be used to compare geometric mean of titers (GMTs), for dengue serotypes 1, 2, 3, and 4, 28 days after the first injection of CYD dengue vaccine between Group 1 and Group 2 for each serotype “i” based on the following individual hypotheses:

$$H_0^i: \text{GMT}_{Group1}^i / \text{GMT}_{Group2}^i \leq \frac{1}{\delta} \Leftrightarrow \log_{10}(\text{GMT}_{Group1}^i) - \log_{10}(\text{GMT}_{Group2}^i) \leq -\log_{10}(\delta)$$

$$H_1^i: \text{GMT}_{Group1}^i / \text{GMT}_{Group2}^i > \frac{1}{\delta} \Leftrightarrow \log_{10}(\text{GMT}_{Group1}^i) - \log_{10}(\text{GMT}_{Group2}^i) > -\log_{10}(\delta)$$

with:

i, serotypes in {1, 2, 3, 4}.

δ , non-inferiority limit is set at 2, i.e., 0.301 ($=\log_{10} [2]$), for each serotype “i”.

Non-inferiority for serotype “i” will be demonstrated if the lower bound of the 2-sided 95% CI is greater than $-\delta$.

Global hypotheses for non-inferiority on CYD response after one dose:

H_0^G : at least one H_0^i not rejected

H_1^G : all H_0^i are rejected

Overall, non-inferiority among the groups will be demonstrated if, for each antigen of Tdap and each serotype of CYD dengue vaccine, the two-sided 95% CI lies above $-\delta$.

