5.5 Determination of Sample Size and Power Calculation

Power calculation is based on initial sample size of the trial. 688 subjects were to be enrolled regardless of dengue baseline status: 344 subjects per treatment group (86 subjects per age group).

Considering a potential attrition rate of 10%, such sample size would provide 618 evaluable subjects in the PPAS of Tdap and CYD dengue vaccine (PPT and PPC). This will give, for the co-primary objectives, a global power over 90.0% for the testing of non-inferiority (based on SAS proc Power).

The following assumptions were considered for the non-inferiority on Tdap: an alpha level of 2.5% (one-sided hypotheses), a maximum acceptable difference of 0.176 for GMCs, and of 10% for seroprotection rates, and assuming the following rates and standard deviations (SDs):

- $T \geq 0.1$ IU/mL – 99% of subjects
- $D \geq 0.1$ IU/mL – 99% of subjects
- PT SD – 0.4
- FHA SD – 0.4
- PRN SD – 0.5
- FIM2+3 SD – 0.6

(based on TD519, TD506 and TD526 studies and on Keith S. Reisinger (4)).

The following assumptions were considered for the non-inferiority after the first dose of CYD dengue vaccine: an alpha level of 2.5% (one-sided hypotheses), a maximum acceptable difference of 0.301 for GMTs, and assuming a standard deviation of 1.0 for serotype 1, 0.8 for serotypes 2 and 3, 0.7 for serotype 4 (based on CYD22 and CYD47 studies conducted in Asia Pacific).

In addition, this sample size would have given for the non-inferiority after the third dose* of CYD dengue vaccine (on PPC3), considered as a secondary objective, a global power over 99.0% for the testing of non-inferiority (based on SAS proc Power).

The following assumptions were considered for the non-inferiority after the third dose* of CYD dengue vaccine: an alpha level of 2.5% (one-sided hypotheses), a maximum acceptable difference of 0.301 for GMTs, and assuming a standard deviation of 0.8 for serotypes 1 and 2, 0.7 for serotypes 3 and 4 (based on studies conducted in Asia Pacific).

* Analysis on the 3rd dose will not be done due to the early termination of study (cf. section 5.7)

Table 5.2: Powers for Non-inferiority between GMT/seroprotection for each antigen and serotype - Primary objective

Antigen/Serotype	Alpha	δ	Reference rate/SD	Power (%) for 309 evaluable subjects per group
D	0.025	10%	99%	> 99.9
T	0.025	10%	99%	> 99.9
PT	0.025	0.176	0.4	> 99.9
FHA	0.025	0.176	0.4	> 99.9
PRN	0.025	0.176	0.5	99.2
FIM2+3	0.025	0.176	0.6	95.4

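### The primary decision sentences set limits that do not match the scale of the pertussis interval or the symbol δ in the hypotheses, although the intended margins are clear elsewhere in the plan

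*SAP*

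**What the plan says.** SAP 5.1.1.1 and Protocol 12.1.1.1 contain three layers for the primary comparisons.

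- **Hypotheses.** For pertussis and dengue, H0 is a Group 1 to Group 2 ratio at or below 1/δ, stated as equivalent to a log10 difference at or below −log10(δ). For tetanus and diphtheria, H0 is a rate difference at or below −δ.
- **Margins.** For pertussis, "non-inferiority limit is set at 1.5, i.e., 0.176"; for dengue, "non-inferiority limit is set at 2, i.e., 0.301"; for tetanus and diphtheria, 10%.
- **Decision sentences.** For pertussis, the lower bound of the 95% "confidence interval (CI) is greater than δ", with no minus sign, and the method rests on the "use of the age-stratified two-sided 95% CI of the ratio of GMCs between groups". For dengue, tetanus and diphtheria the lower bound must exceed −δ. The overall rule requires that "for each antigen of Tdap and each serotype of CYD dengue vaccine, the two-sided 95% CI lies above" −δ.

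The protocol synopsis prints −δ for pertussis, followed directly by the same description of the interval as one for the GMC ratio. SAP 5.1.1.2 and Protocol 12.1.1.2 describe the GMC and GMT tests as intervals for differences of log10 means. SAP 5.5 and Protocol 12.5 take 0.176 and 0.301 as the maximum acceptable differences, with "an alpha level of 2.5% (one-sided hypotheses"), and the δ column of SAP Tables 5.2 and 5.4 lists 0.176, 0.301 and 10%.

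**The concern.** A non-inferiority decision needs an interval, a limit and a common scale. Here one symbol carries a ratio value and its log10 value, and the decision sentences do not say which applies. For pertussis the interval is named on the ratio scale, while the limit is ±δ, a form that fits a log10 or a rate difference. The pattern suits tetanus and diphtheria, where hypothesis and rule both use −10% on a rate difference. The overall rule applies that pattern to eight comparisons (four pertussis antigens, four dengue serotypes) whose hypotheses are in −log10(δ).

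At stake is the pre-specified pass mark for most of the co-primary family and for the overall claim. In an open-label trial with a single final analysis, that mark should not depend on which of several conflicting values a reader picks.

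**Working it through.** **1. Reproduce the plan's power figures, to see which margins were meant.** Inputs from SAP 5.5 and 5.7: one-sided alpha 0.025, true difference 0, log10 SDs of 0.4, 0.4, 0.5 and 0.6 (PT, FHA, PRN, FIM2+3) and 1.0, 0.8, 0.8 and 0.7 (dengue 1 to 4), margins 0.176 and 0.301, and n = 309 or 255 per group. SE = SD × √(2/n); power ≈ Φ(margin/SE − 1.96).

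- FIM2+3, n = 309: SE = 0.6 × √(2/309) = 0.0483; Φ(0.176/0.0483 − 1.96) = 95.4% (stated 95.4).
- FIM2+3, n = 255: SE = 0.0531; 91.2% by this formula, 91.1% by noncentral t (stated 91.1).
- Dengue 1, n = 309: SE = 0.0805; 96.3%, or 96.2% by noncentral t (stated 96.2). At n = 255: SE = 0.0886; 92.5%, or 92.4% (stated 92.4).
- Product of all ten powers: 90.3% at 309 per group and 80.1% at 255 (stated 90% and 80%).

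The power calculation therefore rests on log10 limits of −0.176 and −0.301.

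**2. Pertussis: the written limits against the named interval.** H0 with δ = 1.5 puts the boundary at a GMC ratio of 1/1.5 = 0.667, or −0.176 on log10. For an interval of the ratio:

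- Limit +1.5 (antigen-level sentence, ratio value of δ): the interval must show at least a 1.5-fold gain. For FIM2+3 at 255 per group the half-width is 1.96 × 0.0531 = 0.104 on log10, so the observed difference must exceed 0.176 + 0.104 = 0.280, a ratio of 10^0.280 = 1.9. That is about 0.280/0.0531 = 5.3 standard errors above equality, so at true equality the rule is almost impossible to meet.
- Limit +0.176 (same sentence, log10 value of δ): the boundary is a ratio of 0.176, where 0.667 is needed.
- Limit −1.5 or −0.176 (overall rule and synopsis): a ratio is positive, so the condition always holds.

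None of these is 0.667. If the interval is instead put on log10, +0.176 still demands a 1.5-fold gain, −1.5 is a ratio of 10^−1.5 = 0.032, and only −0.176 gives 0.667. Sign and scale must therefore be corrected together: adding the minus sign while keeping the ratio interval turns a rule that can hardly be met into one that is always met.

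**3. Dengue: one symbol, two values.** The interval is already on the log10 difference (SAP 5.1.1.2).

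- δ = 2: the H0 boundary is a ratio of 1/2 = 0.5, or −0.301 on log10, which is right; the decision limit −δ becomes −2, which is not −0.301.
- δ = 0.301: the decision limit −δ = −0.301 is right; the H0 boundary becomes 1/0.301 = 3.32, which is not 0.5.

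No single value makes both lines correct. The decision rule works only with the 0.301 listed under δ in Tables 5.2 and 5.4.

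**4. Tetanus and diphtheria.** Hypothesis, interval and limit are all on the rate difference with −10%. There is no conflict.

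**The case against.** The best defence is that this is notation and the plan fixes the test several times over. H0 and H1 are correct with δ as a ratio. SAP 5.1.1.2, the methods section, says the test uses differences of log10 means. The ANOVA is run on log10 values, so its native interval is on that scale and a ratio interval is only the back-transform. The δ column of the power tables shows 0.176 and 0.301, and with those values −δ on the log10 difference is exactly the intended limit. For dengue the plan gives 0.301 beside 2, so the right rule can be read directly from the text.

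Most of this stands. It settles what the margins are and leaves dengue as an ambiguity of symbol. It does not rescue the pertussis wording. The antigen-level sentence in SAP 5.1.1.1 and Protocol 12.1.1.1 has the wrong sign on any scale, and the synopsis and overall rule have the wrong limit for a ratio. SAP 5.1.1.2 does not mention age stratification, so the more specific description of the pertussis interval remains the age-stratified ratio, for which no decision sentence states 0.667.

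Two stronger readings are tempting. A reader might infer that the pertussis test cannot fail, because any ratio exceeds −δ. But all individual null hypotheses must also be rejected, and the antigen-level rule of exceeding +δ, with 1.5 on the ratio, can hardly be met at equality. The literal text contradicts itself; it is not unfailable. A reader might also infer that the dengue rule tolerates a 100-fold loss (10^−2 = 0.01). That requires putting the ratio value 2 on a log10 interval, against the H0 printed with it and the 0.301 given in the same line and in the tables.

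**Conclusion.** The concern holds as a defect in the written decision rules. For pertussis, the sentences name a ratio interval and give limits (±1.5 or ±0.176) that are not the 0.667 required by H0, and they contradict one another. For dengue, the symbol δ serves two incompatible purposes, and the rule is right only when 0.301 is taken. Eight of the ten co-primary comparisons and the overall claim depend on these sentences, so the correction is more than clerical.

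It does not show an invalid margin or an invalid analysis. This rests on taking the hypotheses, SAP 5.1.1.2 and SAP 5.5 as the intended test, which the reproduced global powers (90.3% and 80.1%) support. On that basis margins, alpha, power and the threshold of 510 evaluable subjects are unaffected.

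**What to change.** In SAP 5.1.1.1, Protocol 12.1.1.1 and the protocol synopsis, keep δ = 1.5 and δ = 2 as ratio limits only, and write each rule on the scale of its interval:

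- **Pertussis (PT, FHA, PRN, FIM2+3):** lower 95% bound of the age-stratified difference in log10 GMC above −log10(1.5) = −0.176, equivalently a GMC ratio above 0.667.
- **Dengue serotypes 1 to 4:** lower 95% bound of the difference in log10 GMT above −log10(2) = −0.301, equivalently a GMT ratio above 0.5.
- **Tetanus and diphtheria:** lower 95% bound of the rate difference above −10%.
- **Overall rule:** replace the single −δ with a statement that each lower bound exceeds its own limit as listed.

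In the power tables, relabel the δ column as the limit on the analysis scale, so that 0.176 and 0.301 no longer share a symbol with 1.5 and 2. This one rewrite also cures the missing minus sign.

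The cost is a few lines of text, to be settled before database lock. It needs no new data and changes no margin, alpha, power or sample-size figure.

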5.1.1.2 Statistical Methods

Non-inferiority on Tdap vaccine

The non-inferiority test will be performed using the 95% 2-sided CI of the difference between Group 1 and Group 2 for seroprotection rates and of the differences of the means of the \log_{10} transformed post-vaccination concentrations/titers for GMCs/GMTs ($\alpha=2.5\%$ one-sided). The 95% CIs will be calculated based on the Wilson score method without continuity correction as quoted by Newcombe (3) for seroprotection rates and using normal approximation of log-transformed titers for GMCs/GMTs.

Non-inferiority on CYD dengue vaccine after one dose

The statistical methodology will be based on the use of the two-sided 95% CI of the differences of the means of the \log_{10} transformed post-vaccination titers between Group 1 and Group 2. The CI for differences will be calculated using normal approximation of log-transformed titers.

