| Statistical Methods: | 
Non inferiority testing will only be carried out with seropositive subjects and providing that the number of evaluable subjects attains a global power of at least 80%. This applies to the co-primary objectives, and the secondary objective. Otherwise, descriptive analyses will be performed.
 
Primary Objectives:
 
Tdap immunogenicity
 
A non-inferiority testing approach will be used to compare geometric mean concentrations (GMCs) for PT, FHA, PRN, FIM2+3, 28 days after the booster dose of Tdap, for each antigen “i” based on the following individual hypotheses:
 $H_0^i: \text{GMC}_{\text{Group1}}^i / \text{GMC}_{\text{Group2}}^i \leq \frac{1}{\delta} \Leftrightarrow \log_{10}(\text{GMC}_{\text{Group1}}^i) - \log_{10}(\text{GMC}_{\text{Group2}}^i) \leq -\log_{10}(\delta)$ $H_1^i: \text{GMC}_{\text{Group1}}^i / \text{GMC}_{\text{Group2}}^i > \frac{1}{\delta} \Leftrightarrow \log_{10}(\text{GMC}_{\text{Group1}}^i) - \log_{10}(\text{GMC}_{\text{Group2}}^i) > -\log_{10}(\delta)$ 
with:
 
i, antigen {PT, FHA, PRN, FIM 2+3}.
 
<math>\delta</math>, non-inferiority limit is set at 1.5, i.e., 0.176 (<math>=\log_{10} [1.5]</math>), for each antigen “i”.
 
Non-inferiority for antigen “i” will be demonstrated if the lower bound of the 2-sided 95% CI is greater than <math>-\delta</math>. For each of the 4 antigens, the statistical methodology will be based on the use of the age-stratified two-sided 95% CI of the ratio of GMCs between groups. The age-stratified CI will be calculated using an ANOVA model (type II analysis) of <math>\log_{10}</math>-transformed titers. The age groups (9 to 11 years, 12 to 17 years, 18 to 45 years and 46 to 60 years) will be used as the stratifying factor in the model.
 
Additionally, a non-inferiority testing approach will be used to compare seroprotection rates of T and D, 28 days after the booster dose of Adacel®. Seroprotection is defined as anti-D and anti-T Ab concentration superior to 0.1 IU/mL.
 
The individual tested hypotheses for the antigen “i” will be as follows:
 $H_0^i: P_{\text{Group1}}^i - P_{\text{Group2}}^i \leq -\delta$ $H_1^i: P_{\text{Group1}}^i - P_{\text{Group2}}^i > -\delta$ 
Where the non-inferiority limit <math>\delta</math> is set at 10% for both T and D concentrations <math>\geq 0.1</math> IU/mL.
 
Non-inferiority for antigen “i” will be demonstrated if the lower bound of the 2-sided 95% CI is greater than <math>-\delta</math>.
 
The non-inferiority test will be performed using the 95% 2-sided CI of the difference between Group 1 and Group 2 for seroprotection rates and of the differences of the means of the <math>\log_{10}</math> transformed post-vaccination concentrations/titers for GMCs (<math>\alpha=2.5\%</math> one-sided). The 95% CI will be calculated based on the Wilson score method without continuity correction as quoted by Newcombe for seroprotection rates and using the normal approximation of the <math>\log_{10}</math> transformed post-vaccination titers for GMCs.
 
CYD dengue vaccine immunogenicity
 
A non-inferiority testing approach will be used to compare geometric mean titers (GMTs), for dengue serotypes 1, 2, 3, and 4, 28 days after the first injection of CYD dengue vaccine between Group 1 and Group 2 for each serotype “i” based on the following individual hypotheses:
 $H_0^i: \text{GMT}_{\text{Group1}}^i / \text{GMT}_{\text{Group2}}^i \leq \frac{1}{\delta} \Leftrightarrow \log_{10}(\text{GMT}_{\text{Group1}}^i) - \log_{10}(\text{GMT}_{\text{Group2}}^i) \leq -\log_{10}(\delta)$ $H_1^i: \frac{1}{\delta} < \text{GMT}_{\text{Group1}}^i / \text{GMT}_{\text{Group2}}^i > \frac{1}{\delta} \Leftrightarrow \log_{10}(\text{GMT}_{\text{Group1}}^i) - \log_{10}(\text{GMT}_{\text{Group2}}^i) > -\log_{10}(\delta)$ |

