## **6.5 Randomization and Allocation Procedures**

Subjects will be randomized in a 1:1 ratio into Group 1 or Group 2. Stratification according to age will be applied (9 to 11 years, 12 to 17 years, 18 to 45 years and 46 to 60 years) to balance the potential difference in terms of booster response by age group for the pertussis antigens (PT, FHA, PRN and FIM2+3).

The full detailed procedures for randomization are described in the Operating Guidelines.

Subject numbers will be 8 digits long, with a 3-digit center identifier and a 5-digit subject identifier. For example, Subject 001-00001 is the first subject enrolled in center number 1 and Subject 002-00001 is the first subject enrolled in center number 2.

Subject numbers will be an 8-digit string, consisting of a 3-digit study center identifier and a 5-digit subject identifier. The 5-digit subject identifier will correspond to the age group (the first digit will be used to identify the age group, with “0” for subjects aged 9 to 11 years, “1” for subjects aged 12 to 17 years, “2” for subjects aged 18 to 45 years, and “3” for subjects aged 46 to 60 years) and to chronological order of enrollment in the center. Subject identifier will be:

- From 00001 to 09999 for subjects aged 9 months through 11 years
- From 10001 to 19999 for subjects aged 12 years through 17 years
- From 20001 to 29999 for subjects aged 18 years through 45 years
- From 30001 to 39999 for subjects aged 46 years through 60 years

For example, Subject 001-10001 is the first subject in the 12-17 year-old age group enrolled in the study center number 1 and Subject 002-20001 is the first subject from the 18-45 year-old age group enrolled in the study center number 2.

Subject numbers should not be reassigned for any reason.

The Statistical Platform of the Sponsor will provide scratchable randomization lists (one per site). These lists will mention the randomization number of the subject and the corresponding study group covered by a silver-colored patch. After subject number allocation to a subject, the Investigator will scratch off the list to know the study group. Once scratched, each randomization line will be dated and signed by the Investigator or the sub-Investigator in charge of administering the study vaccine(s).

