3.1 Trial Design

This is a Phase IIIb, randomized, open label, multicenter study in 688 healthy subjects aged 9 to 60 years in the Philippines.

Subjects were to receive the CYD dengue vaccine according to a 3-dose schedule, given 6 months apart. A booster dose of Tdap vaccine (Adacel®) was to be administered either concomitantly to or before (sequential administration) the first dose of CYD dengue vaccine.

Subjects were to be randomized according to a 1:1 ratio into one of the 2 following groups with stratification on age (9 to 11 years, 12 to 17 years, 18 to 45 years and 46 to 60 years):

- **Group 1:** subjects were to be administered the first dose of CYD dengue vaccine concomitantly with the booster dose of Tdap vaccine at the second visit (V02; M1)
- **Group 2:** subjects were to receive Tdap vaccine at the first visit (V01; D0), and then CYD dengue vaccine 28 days later at the second visit (V02; M1)

The stratification was to be considered in order to balance the potential difference in terms of booster response by age group for the pertussis antigens (PT, FHA, PRN and FIM2+3).

Since the CYD dengue is to be administered according to a 3-dose schedule, given 6 months apart, initial trial design included administration of the second and third doses of CYD dengue vaccine at V04 (Month 7 [M7] and at V06 (M13) in all subjects.

At the time of study hold linked to the recommendation from IDMC not to vaccinate seronegative individuals anymore based on the results of the exploratory case-cohort study, all but 19 subjects (from both, Group 1 and Group 2) did receive dose 2 of the CYD dengue vaccine as planned. Following the IDMC recommendations, Sanofi Pasteur paused all vaccinations in CYD66 study, determined baseline serostatus and the Principal Investigators have communicated serostatus information to subjects already included in the study. In addition, the study protocol was amended to reflect the IDMC recommendations. The Sponsor has not received any feedback nor approval for the protocol amendment from Philippines FDA and has therefore decided to put an end to the CYD66 study with a last visit (which served as termination visit) of the subjects in order to inform them of the end of the study and to perform the last safety follow up. As a consequence, no more CYD dengue vaccine were administered to any subjects included in the study since the study hold. More details will be mentioned in the CSR

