4.4.5 Baseline Dengue status

The dengue status at baseline is defined as the presence of Abs against at least one dengue serotype in the baseline sample (by dengue 50% plaque reduction neutralization test [PRNT₅₀] in the BL collected at V02 (BL) from all subjects. The baseline dengue status variable will be calculated for each subject as follows:

- Dengue immune subjects at baseline (seropositive) are defined as those subjects with titers ≥ 10 (1/dil) for at least one serotype with the parental dengue virus strain
- Dengue non-immune subjects at baseline (seronegative) are defined as those subjects with titers < 10 (1/dil) (not quantified) for all serotypes with parental dengue virus strains with available “valid” results (i.e. different from missing or ”NR”)
- Otherwise the baseline status will be classified as undetermined and subjects will have their dengue baseline status derived as non-immune.

5 Statistical Methods and Determination of Sample Size

The analysis will be performed under the responsibility of the Sponsor’s Biostatistics platform with the SAS software, version 9.4 or higher (SAS Institute, Cary, North Carolina, USA).

The results of the statistical analysis will be available in the final clinical study report (CSR).

For descriptive purposes, the following statistics will be presented:

Table 5.1: Descriptive statistics produced

Baseline	Categorical data	Number of subjects.
----------	------------------	---------------------

characteristics and follow-up description		Percentage of subjects.
	Continuous data	Mean, standard deviation, quartiles, minimum, and maximum.
Clinical safety results	Categorical data	Solicited: Number and percentage (95% confidence interval [CI]) of subjects. Unsolicited: Number and percentage (95% CIs) of subjects, and number of events.
Immunogenicity results	Categorical data (cutoff)	Number and percentage (95% CIs) of subjects.
	Continuous data (titer / titer ratio)	Log10: Mean and standard deviation. Anti-Log10 (work on Log10 distribution, and anti-Log10 applied): Geometric mean, 95% CI of the geometric mean, quartiles, minimum, and maximum. Graphical representation by Reverse Cumulative Distribution Curve (RCDC).

The CI for the single proportion will be calculated using the exact binomial method (Clopper-Pearson method, quoted by Newcombe (2), i.e., using the inverse of the beta integral with SAS®).

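### The co-primary dengue interval leaves out the age strata used to randomise; it is valid but conservative if age predicts titre, and adding them gains modest power

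*SAP*

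**What the plan says.** Protocol 6.5 sets 1:1 randomisation within four age groups (9 to 11, 12 to 17, 18 to 45 and 46 to 60 years): "Stratification according to age will be applied". SAP 3.1 gives the reason for stratifying: "in order to balance the potential difference in terms of booster response by age group for the pertussis antigens".

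For the four pertussis GMCs, SAP 5.1.1.1 puts age in the model: "The age-stratified CI will be calculated using an analysis of variance (ANOVA) model (type II analysis". The Statistical Methods part of the Protocol Synopsis specifies the same model: "The age-stratified CI will be calculated using an ANOVA model (type II analysis".

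For the four dengue GMTs 28 days after dose 1, SAP 5.1.1.2 and Protocol 12.1.1.2 use the difference in mean log10 titres between groups, with no age term: "The CI for differences will be calculated using normal approximation of log-transformed titers". For dengue, age appears only in a descriptive breakdown by age group (SAP 5.1.2.2).

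The Tdap paragraph of SAP 5.1.1.2 describes the pertussis interval as obtained "using normal approximation of log-transformed titers for GMCs/GMTs". It neither mentions the age strata nor refers back to 5.1.1.1.

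**The concern.** Stratified randomisation balances age between the groups by design. The estimated difference in mean log10 titre therefore varies only with the spread of titres within age groups. An interval without age still uses the total spread, including the part due to age. If age predicts dengue titre, the interval is too wide for the design and the test is less likely to pass than its nominal level allows.

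This bears on the overall conclusion because all six Tdap antigens and all four serotypes must pass (SAP 5.1.1.1). At 255 per group the two weakest endpoints in SAP Table 5.4 are FIM2+3 (91.1%) and dengue serotype 1 (92.4%). FIM2+3 already has the age-stratified model; serotype 1 does not. The reason given for stratifying concerns pertussis only. It explains why the strata exist, not why they are left out of the dengue interval.

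**Working it through.** **Inputs from the documents.** One-sided alpha 0.025. Dengue margin 0.301, with SDs 1.0, 0.8, 0.8 and 0.7 for serotypes 1 to 4. Pertussis margin 0.176, with SDs 0.4 (PT), 0.4 (FHA), 0.5 (PRN) and 0.6 (FIM2+3). T and D seroprotection 99%, margin 10% (SAP 5.5). Evaluable subjects per group: 309 planned, 255 the minimum for testing (SAP 5.7). Seropositive dose 1 recipients: 629 (SAP 1).

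**Assumptions.** True difference zero, which reproduces the tables. Planning SDs are total SDs. Groups are balanced within strata. Endpoints are independent, so global power is a product. Age explains a share R² of log10 variance, the same for every log10 endpoint. The documents give no value, so 2%, 10% and 20% are shown.

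**Step 1: reproduce the plan without age.** For serotype 1 at 255, SE = 1.0 × √(2/255) = 0.0886 and noncentrality = 0.301/0.0886 = 3.40. The noncentral t gives 92.4%, as tabled. The product at 255 (T and D ≈ 1) is 0.9986 × 0.9986 × 0.9776 × 0.9108 × 0.9240 × 0.9887 × 0.9887 × 0.9981 = 80.1%. At 309 it is 90.3%. Both match SAP Table 5.4.

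**Step 2: one-sided size and width of the unadjusted dengue interval.** Under stratified randomisation the estimate has SD equal to SD × √(1−R²) × √(2/n), while the interval uses the full SD. Size is P(Z > 1.96/√(1−R²)), and width relative to the adjusted interval is 1/√(1−R²).

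| R² | 1.96/√(1−R²) | One-sided size | Excess width |
|---|---|---|---|
| 2% | 1.980 | 2.39% | 1% |
| 10% | 2.066 | 1.94% | 5% |
| 20% | 2.191 | 1.42% | 12% |

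Simulation of serotype 1 (60,000 trials, 64 per stratum per group) gave sizes of 2.34%, 2.02% and 1.50% without age, and 2.46%, 2.61% and 2.53% with age.

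**Step 3: serotype 1 power at 255, R² = 10%.** By normal approximation, unadjusted power is Φ((3.40 − 1.96)/√0.9) = 93.5% and adjusted power is Φ(3.40/√0.9 − 1.96) = 94.8%. Simulation gave 93.5% and 94.7%.

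**Step 4: global power, dengue interval as planned versus with age.** Adjusted power uses the noncentral t with SD × √(1−R²) and 2n − 5 degrees of freedom. Unadjusted power uses the estimate's SD from step 2 with the pooled variance that ignores age. The 283 row is 629 × 0.9 / 2, taking an assumed 10% loss.

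| Setting | R² = 2% | R² = 10% | R² = 20% |
|---|---|---|---|
| Four dengue endpoints, 255 | 90.5 → 90.9% | 91.8 → 93.5% | 93.4 → 96.1% |
| Global, 255, pertussis with age | 81.0 → 81.4% | 84.7 → 86.3% | 89.0 → 91.5% |
| Global, 255, pertussis at planning power | 80.4 → 80.7% | 81.5 → 83.0% | 83.0 → 85.4% |
| Global, 283, pertussis with age | 87.0 → 87.3% | 89.9 → 91.0% | 93.1 → 94.8% |

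**Step 5: effect on the bar.** At 255, the lowest serotype 1 GMT ratio that passes is 10^(−0.301 + half-width). Without age this is 0.746. With age it is 0.743, 0.731 or 0.716.

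**The case against.** The strongest case is that nothing here is wrong. The dengue interval is fully specified, valid and conservative. The sample size, the 510-subject threshold and the planned interval agree with one another. The omission cannot produce a false claim of non-inferiority. The pertussis-only purpose of stratifying also suggests why age was used for one vaccine and not the other. All of that stands, and it makes this a point of efficiency and consistency. It does not remove the conservatism, which follows from how subjects were allocated, whatever the reason for stratifying.

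The size of the benefit also rests on an R² that the documents do not give, least of all for the seropositive subjects now analysed. If age has no effect, nothing is lost. The largest gain, 2.5 points, needs both R² = 20% and the minimum number of subjects. With 629 seropositive recipients the evaluable number may be nearer 283 per group, where the gain is about 0.3, 1.1 or 1.7 points. The Tdap tests, mainly FIM2+3, also cap global power: at their planning power it cannot exceed 88.8% at 255 per group. These limits are real.

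The most serious objection concerns timing. The change makes a primary criterion slightly easier to meet, in an open-label trial, under a SAP that cites June 2019, after dosing had ended. SAP 5.7 says the first interim analysis was not done, so the documents report no earlier comparison by group. That does not prove that nobody has seen titres by group, and the documents do not say whether the database has been locked. The change is therefore acceptable only under the conditions set out in the fix.

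The descriptive dengue results by age group would show an age pattern, but they do not replace a stratified test.

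**Conclusion.** The concern holds. The dengue co-primary interval ignores the strata used in randomisation, while the pertussis intervals in the same decision rule use them. The consequence is possible conservatism, not bias or a power shortfall. Under the assumptions above, the dengue test runs at 1.42% to 2.39% instead of 2.5%, and adding age raises global power by 0.3 to 2.5 points across the scenarios shown. The direction is certain if age predicts titre; the amount depends on an R² that must be assumed. This is a worthwhile improvement at little cost. The missing cross-reference for the pertussis interval is a minor editorial point: the wording can be read as compatible with 5.1.1.1, but it does not say so. The T and D intervals are not affected.

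**What to change.** If the database is not locked and no V03 dengue titre has been summarised by group:

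- In SAP 5.1.1.2, make the pertussis model primary for the four dengue GMTs: log10 post-dose titre on group and four-level age stratum, with the model-based two-sided 95% CI for Group 1 minus Group 2. Compare the lower bound with −0.301, as now.
- Use the same model for the FAS confirmation in dengue-immune subjects (SAP 5.2.5).
- Keep the protocol's unadjusted dengue interval as a sensitivity analysis.
- Record the change in SAP 5.7 with its reason, stating that it slightly lowers the passing ratio.

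If titres by group have already been seen, keep the unadjusted interval primary and report the age-adjusted one as supportive.

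In either case, add one sentence to SAP 5.1.1.2 stating that the age-stratified ANOVA of 5.1.1.1 governs the four pertussis GMCs. Leave T and D unchanged.

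The cost is one model statement, one cross-reference and one entry in 5.7. No new data are needed, because the stratum is coded in the five-digit subject identifier (Protocol 6.5): "the first digit will be used to identify the age group". Nobody leaves the analysis because of the covariate. Subjects without a valid baseline dengue result are already outside the per-protocol dengue analysis, since SAP 4.4.5 treats them as non-immune: "Otherwise the baseline status will be classified as undetermined and subjects will have their dengue baseline status derived as non-immune". The real cost is having to justify a late change.
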